7.3.3.2 Secondary Outcomes

- **Hypoxemia**—Sample size permitting, hypoxemia (i.e., oxygen saturation [SpO₂] <90%) will be captured as available in the database using specific ICD-10-CM codes or EHR data among the subset of patients with both claims and EHR in the Market Clarity database. Time to hypoxemia will be reported as time between index date and first evidence of hypoxemia.
- **Respiratory deterioration/Acute exacerbations**—An acute exacerbation of fibrosing ILD has been defined clinically as an unexplained worsening or development of dyspnea within 30 days in combination with a high-resolution CT indicating interstitial pneumonia, and excluding pulmonary infection, left heart failure, pulmonary embolism or other identifiable causes of acute lung injury.⁹ Based on these clinical criteria, acute exacerbations will be defined as follows:
 - ≥1 claim with procedure code for CT scan, and
 - Evidence of dyspnea, as defined by ICD-10-CM codes or EHR data in the integrated database, within 30 days prior to date of CT scan, and
 - No claims with diagnosis for pulmonary infection, left heart failure, pulmonary embolism, or other identifiable causes of acute lung injury within 30 days prior to date of CT scan.

The time to first exacerbation and population annualized counts of exacerbations (sum of all exacerbations for all individuals / sum of follow-up time [person years] for all individuals) will be described. Exacerbations occurring within 14 days of each other will be considered a single exacerbation episode. The start date of the exacerbation episode will be the service date of the first event (i.e., dyspnea or CT scan). The end date of the exacerbation episode will be defined as the last observed exacerbation event date (or discharge date if event occurs during an inpatient stay) + 14 days. Exacerbation episodes that include an inpatient stay will also be reported separately as exacerbations involving a hospitalization.

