5. RATIONALE AND BACKGROUND

Interstitial lung disease (ILD) is a broad term that describes more than 200 diverse lung disorders, including idiopathic pulmonary fibrosis (IPF), autoimmune ILD, hypersensitivity pneumonitis (HP), and sarcoidosis.¹ Typical symptoms of ILD include cough and dyspnea, as well as decreased lung capacity², which leads to exercise intolerance and hypoxemia.

The major goal of therapy in ILD patients is to slow disease progression as well as improve the associated dyspnea, exercise capacity, and health-related quality of life.³ Approved treatment options for fibrosing ILD comprise antifibrotic treatments including nintedanib and pirfenidone, which slow the rate of decline in forced vital capacity (FVC). Other commonly prescribed treatment options are corticosteroids, immunosuppressants, opioids, and lung transplantation.⁴ Despite advances in pharmacotherapy, many patients continue with disease progression. Oxygen therapy is commonly administered to reduce breathlessness and increase physical capacity by improving gas exchange.⁵

Supplemental oxygen (O₂) is commonly prescribed in clinical practice for patients with fibrotic ILD; however, robust evidence to support its long-term use is lacking. Recommendations for long-term oxygen therapy (LTOT) for resting hypoxemia in ILD are largely extrapolated from trials conducted in chronic obstructive pulmonary disease (COPD), where a survival benefit is well established.^{6,7} The American Association for Respiratory Care guideline recommends the use of oxygen therapy to maintain the oxygen saturation (SpO₂) range of 94–98% for most hospitalized patients.⁸ Despite its frequent use, there is a paucity of studies evaluating the incidence, prevalence, and impact of LTOT on outcomes such as disease progression or mortality in ILD. This study will help fill in the gaps in increasing the understanding of the use of oxygen therapy among fibrosing ILD patients and assess whether the use of oxygen leads to better or worse outcomes.

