7.2.3 Study population: Aim 2 [REDACTED]

The analysis for Aim 2 and Further Aim will include patients identified for Aim 1 in Section 7.2.2 who meet the following additional selection criteria. Final oxygen therapy cohorts will be determined during the propensity score matching (PSM) procedure outlined in Section 7.6.2.2.

- **Oxygen therapy cohort**

- ILD patients with ≥ 1 medical claim for oxygen therapy after fibrosing ILD diagnosis. The ***index date*** will be defined as the first date of a claim for oxygen therapy.

- **No oxygen therapy cohort**
 - Matched to a patient in the oxygen therapy cohort. The **index date** will be assigned as a date that is eligible to set an index date (i.e., similar to the matched oxygen therapy patient in time from the fibrosing ILD diagnosis date to the index date, and during the same continuous enrollment period as the fibrosing ILD diagnosis date).

NOTE: Following review of results from Aim 1, the study team will determine whether criteria for Aim 2 and Further Aim require revision.

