7.3 VARIABLES

Variables related to the study period will be defined as follows:

Aim 1

- **Fibrosing ILD diagnosis date**—The first ILD diagnosis date for patients with ≥ 2 fibrosing ILD diagnoses on different dates and within 365 days. The fibrosing ILD diagnosis date is the first day of follow-up observation time for Aim 1.
- **Pre-ILD baseline period**—The 12-month period prior to the fibrosing ILD diagnosis date.
- **Aim 1 follow-up period**—The variable period starting on the fibrosing ILD diagnosis date and continuing until the earliest of the following: disenrollment from the health plan, death, or end of the study period. The Aim 1 follow-up period will be used to assess Aim 1 outcomes.
 - **All-cause mortality**—Death will be used as a censoring event and is further defined in Section 7.3.3.1.

Aim 2

- **Index date**—For the oxygen therapy cohort, the first date following the fibrosing ILD diagnosis date with a claim with diagnosis for oxygen therapy; for the no oxygen therapy cohort, a date within the same continuous enrollment period as the fibrosing ILD diagnosis date that is similar to the matched oxygen therapy patient in time from fibrosing ILD to index date. The index date is the first day of follow-up observation time for Aim 2 and Further Aim.
- **Pre-index baseline period**—The 12-month period prior to the index date.
- **Aim 2 follow-up period**—The variable period starting on the index date until the earliest of the following: disenrollment from the health plan, death, or the end of the study period. Matched pairs will be given the same duration of follow-up. The Aim 2 follow-up period will be used to assess Aim 2 and Further Aim outcomes.
 - **All-cause mortality**—Death will be used as a censoring event and is further defined in Section 7.3.3.1.

An overview of the analytic study variables and the study periods for which each analytic variable will be reported is provided in Table 1. Additional variable information is provided in Sections 7.3.1 to 7.3.4.

Table 1. Analytic Variables by Data Source and Time Period

Characteristic	Data source		Aim 1 time period		Aim 2 time period	
	Claims*	EHR	Pre-ILD baseline	Follow-up	Pre-index baseline	Follow-up
Aim 1 outcomes						
Oxygen therapy (time to initiation, sustained oxygen therapy use)		X		X	X	
Aim 2 outcomes						
Disease progression	X	X				X
All-cause mortality	X					X
Hypoxemia	X	X	X		X	X
Acute exacerbations	X	X				X
Patient characteristics†						
Index year	X		X		X	

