7.3.1 Aim 1 Outcomes

7.3.1.1 Primary Outcomes

- **Oxygen Therapy**—Evidence of oxygen use will be captured in the pre-ILD baseline and Aim 1 follow-up periods based on the presence of ≥ 1 diagnosis (ICD-10-CM), procedure (HCPCS, CPT), or revenue code for oxygen therapy. Among patients with oxygen therapy in follow-up, the following aspects of oxygen therapy will be described:
 - **Time to oxygen therapy initiation**—The time in days from the fibrosing ILD diagnosis date to oxygen therapy initiation, among patients without evidence of oxygen therapy in the pre-ILD baseline period.
 - **Sustained oxygen therapy use**—Using claims, sustained oxygen therapy use will be defined among patients with at least 12 months of follow-up after the index date (oxygen initiation date), as a binary variable for the presence of ≥ 11 claims for oxygen therapy in a 12-month period. The following aspects of sustained oxygen therapy will be described:
 - **Time to sustained oxygen therapy use**—The time in days between the index date and the earliest date that defined the sustained oxygen therapy use.
 - **Sustained oxygen therapy use within the first 12 months of follow-up**—The number of patients with the evidence of sustained oxygen therapy use during the first 12 months of follow-up.
 - **Note:** As a sensitivity analysis, sustained oxygen therapy use will also be defined as ≥ 6 claims for oxygen therapy in a 12-month period and, based on the distribution of the count of claims among the population, as the 75th percentile of claims in a 12-month period.

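### The hypoxemia outcome counts a diagnosis code or an SpO2 reading after index as the same event, and oxygen treatment can affect both, in opposite directions

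*Combined protocol and SAP*

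**What the plan says.** Section 7.3.3.2 gives hypoxemia a physiological meaning, SpO2 below 90%, and then says it "will be captured as available in the database using specific ICD-10-CM codes or EHR data", among patients who have both claims and EHR. Either source is enough. On timing: "Time to hypoxemia will be reported as time between index date and first evidence of hypoxemia". Nothing in the definition separates coded from measured events, asks for confirmation, or states whether the patient was on oxygen when the reading was taken.

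The clock starts at treatment. In Section 7.2.3 the oxygen cohort's index date "will be defined as the first date of a claim for oxygen therapy", and Section 7.3 adds "The index date is the first day of follow-up observation time for Aim 2 and Further Aim". Comparators are patients who had not yet started oxygen (Section 7.1).

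Section 5 links the exposure to this outcome twice. It refers to "Recommendations for long-term oxygen therapy (LTOT) for resting hypoxemia in ILD", so hypoxemia is a reason for treatment. It also cites a guideline that "recommends the use of oxygen therapy to maintain the oxygen saturation" at 94–98%, for most hospitalized patients, so treatment acts on the measurement.

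The abstract lists time to hypoxemia among the Aim 2 primary outcomes. Section 7.3.3.2 places it among the secondary outcomes, subject to sample size.

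**The concern.** This point concerns events recorded after the index date. How hypoxemia recorded on or before that date should be handled is a separate matter.

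The two sources respond to treatment in different ways:

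- **Codes.** If resting hypoxemia is why oxygen is supplied, later oxygen claims may carry a hypoxemia diagnosis to support payment. Section 7.8 itself says that claims exist for payment. Such a code meets the outcome with no new reading below 90%, which adds events to the oxygen cohort.
- **Readings.** A reading taken on oxygen may stay above 90% in a patient who would be below it on room air. That removes events from the oxygen cohort.

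Propensity matching balances patients at baseline and cannot correct how events are detected afterwards. Section 7.8 acknowledges limited EHR availability, coding error and residual confounding, but not outcome error that differs by exposure.

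The stake is the study's stated purpose of learning whether oxygen leads to better or worse outcomes. On this outcome, an apparent harm or benefit could come from how events were captured.

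**Working it through.** The plan gives no event rate, power or sample size for hypoxemia, so there is no figure to reproduce. The documents establish the mechanism. The numbers below are assumptions that show its range.

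**Inputs from the documents.** The event is SpO2 below 90%, by code or EHR (7.3.3.2). Time runs from the index date to the first evidence (7.3.3.2, 7.3). The index is the first oxygen claim (7.2.3). The cited saturation range on oxygen is 94–98%, above the 90% cut-off (Section 5).

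**Inputs assumed.** q is the share of oxygen claims carrying a hypoxemia code, and three later claims are considered. r is the true 12-month risk, equal in both cohorts. s is the factor by which on-oxygen readings reduce the detectable hazard. c is the share of oxygen patients with at least one supply-only hypoxemia code in the 12 months after index. None of these is given in the documents.

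**Step 1: code route alone.** The chance of at least one coded event on three later oxygen claims depends on how codes cluster within a patient:

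| q | Independent claims, 1−(1−q)³ | Independent, and index claim uncoded, (1−q)[1−(1−q)³] | Code fixed per patient, index claim ignored, q | Code fixed per patient, index-date code counts as the event |
|---|---|---|---|---|
| 10% | 27.1% | 24.4% | 10% | 0% |
| 25% | 57.8% | 43.4% | 25% | 0% |
| 50% | 87.5% | 43.8% | 50% | 0% |

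The third and last columns matter because the outcome is a first event: a patient already counted at index cannot have a later first event. Independence is doubtful for a code repeated to support continuing supply, so the second column is an upper illustration.

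**Step 2: reading route alone.** With an exponential hazard, λ = −ln(1−r), and the oxygen-cohort risk is 1 − exp(−λs) = 1 − (1−r)^s. For r = 20%:

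- s = 0.7: 1 − 0.8^0.7 = 14.5% against 20%, a cumulative hazard ratio of 0.70.
- s = 0.4: 1 − 0.8^0.4 = 8.5% against 20%, a ratio of 0.40.

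Both falsely favour oxygen.

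**Step 3: both routes, no true difference.** If the coded event is independent of true hypoxemia, the 12-month risk is 1 − (1−c)(1−r)^s. This depends on whether a code appears in the year, not when. For r = 20% and c = 10%:

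- s = 1: 1 − 0.9 × 0.8 = 28.0% (ratio 1.47)
- s = 0.7: 23.0% (ratio 1.17)
- s = 0.4: 17.7% (ratio 0.87)

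The same coding share gives apparent harm or apparent benefit, depending on s.

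**Step 4: where the routes cancel.** Setting the risk equal to r gives c = 1 − (1−r)^(1−s). For r = 20% this is 6.5% (s = 0.7) or 12.5% (s = 0.4). For r = 40% it is 14.2% or 26.4%. Above these values the outcome leans against oxygen, and below them in its favour. The combined outcome gives no means of telling on which side the study falls.

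Steps 2 to 4 treat comparators as untreated throughout. Comparators who later start oxygen would narrow these gaps.

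**The case against.** The strongest counter-arguments are these.

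- **Comparators are not immune.** A reader might infer that the comparator rate from supply codes is exactly zero. The documents do not support that. Comparators had only not yet started oxygen, and no visible rule in Section 7.3 ends their follow-up when they do. The asymmetry holds until initiation and then fades. This objection stands.
- **The claim count is not a forecast.** A reader might take "11 claims for oxygen therapy in a 12-month period" in Section 7.3.1.1 to mean that the Aim 2 oxygen cohort will have near-monthly claims. That is a minimum for an Aim 1 sustained-use variable. Section 7.2.3 requires only one oxygen claim. This also stands, so the number of later claims is an assumption here.
- **The coding premise is inferred.** No document says that oxygen claims carry hypoxemia codes. The inference rests on the stated indication and on the payment purpose of claims. The reading route has more direct textual support, although the cited 94–98% range concerns hospitalized patients.
- **Safeguards may exist elsewhere.** Section 7.6.2 and the code lists are not in the public text, so a restriction there cannot be ruled out. The visible text also does not specify a hazard ratio for hypoxemia, and the summary of compared outcomes in Section 7.1 does not name it, although it says outcomes will be modelled. The definition in 7.3.3.2 contains no safeguard, and that is where one belongs.
- **A blunt repair would do harm.** The oxygen list in Section 7.3.1.1 includes diagnosis and revenue codes. Dropping every hypoxemia code on any claim with an oxygen code could delete genuine visits or admissions, mainly in oxygen users. Restricting the comparison to room-air readings would select patients who can be measured off oxygen. Both points stand and limit the fix.
- **Saturation under treatment is a fair question.** It is, provided the result is described that way.

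**Conclusion.** The concern holds for the definition as written. A code or a reading after index counts as the same event, treatment plausibly affects both, and the effects run in opposite directions. A between-cohort comparison of the combined outcome therefore reflects billing and oxygen delivery as well as disease.

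Neither the size nor the sign of the net error can be obtained from the documents. The code route runs from 0% to 87.5% over the assumptions shown. For the two routes together, modest inputs are enough to reverse the apparent direction: 23.0% or 17.7% against a true 20%.

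Two stronger conclusions are not supported. One is that the outcome carries no information on disease: genuine low readings still count. The other is that the bias is known to be large or to favour one cohort.

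The definition should be changed, but the outcome's conditional status and secondary rank in 7.3.3.2 limit the weight of the point. The abstract lists it as primary, and the two places should be reconciled.

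**What to change.** In Section 7.3.3.2:

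1. Make a measured EHR SpO2 below 90% the main definition, which matches the meaning already stated, and report code-only events separately.
2. In the code-based version, do not count a hypoxemia code that appears only on an oxygen supply or equipment claim. Keep codes on visit and inpatient claims.
3. Where the EHR records oxygen status, report room-air and on-oxygen readings separately as a sensitivity analysis. Otherwise describe the outcome as recorded hypoxemia under treatment, and do not interpret it as the course of disease.
4. Add a sentence to Section 7.8 saying that detection may differ by exposure.

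The cost is one claim-level rule and split tables on data already planned. The oxygen code list is needed anyway for Section 7.3.1.1, and Section 7.4 lists vital signs among the EHR elements. Section 7.3.3.2 already limits this outcome to patients with both claims and EHR, so the eligible group does not change. Section 7.8 suggests that claims would fill in for patients without EHR data, and that wording should be aligned.

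The downside is fewer events. Oxygen status will be missing for some readings and is not among the EHR elements listed in Section 7.4, so the third step may prove thin. A measured definition still leaves the masking of readings by treatment, but removes the opposing code route from the main result.

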date (i.e., similar to the matched oxygen therapy patient in time from the fibrosing ILD diagnosis date to the index date, and during the same continuous enrollment period as the fibrosing ILD diagnosis date).

NOTE: Following review of results from Aim 1, the study team will determine whether continuous enrollment criteria for Aim 2 and Further Aim requires revision.

Variables:	
Aim 1
 
Outcomes: time to initiation of oxygen therapy; time to sustained oxygen therapy use; sustained oxygen therapy use within the first 12 months of follow-up
 
Baseline covariates: demographic characteristics (age, sex, race/ethnicity, geographic region, insurance type, index year), clinical characteristics (underlying ILD type; respiratory diseases; other clinical characteristics; Quan-Charlson comorbidity score; Agency for Health Research and Quality [AHRQ] comorbid conditions; smoking; pulmonary rehabilitation) healthcare utilization characteristics (provider specialty; medication use; all-cause HCRU; all-cause health care costs)
 
Stratification: IPF vs non-IPF ILD
 
Aim 2 [REDACTED]
 
Exposure: oxygen therapy vs no oxygen therapy
 
Primary Outcomes: Time to disease progression; time to all-cause mortality; time to hypoxemia, time to acute exacerbations, counts of acute exacerbations
 
[REDACTED]
 
Baseline covariates: demographic characteristics (index year, age, sex, race/ethnicity, geographic region, insurance type), clinical characteristics (underlying ILD type; respiratory diseases; other clinical characteristics; Quan-Charlson comorbidity score; AHRQ comorbid conditions; smoking; pulmonary rehabilitation) healthcare utilization characteristics (provider specialty; medication use; all-cause HCRU; all-cause health care costs)

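### Time to hypoxemia starts on the day of the first oxygen claim with no visible rule for same-day or pre-existing hypoxemia, and the medication covariates name no antifibrotic

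*Combined protocol and SAP*

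**What the plan says.** For the oxygen cohort, Section 7.2.3 says that the index date "will be defined as the first date of a claim for oxygen therapy". Section 7.3 describes Aim 2 follow-up as "The variable period starting on the index date until the earliest of the following" of disenrollment, death or end of study, and adds: "The index date is the first day of follow-up observation time for Aim 2 and Further Aim". Section 7.3.3.2 then defines the endpoint: "Time to hypoxemia will be reported as time between index date and first evidence of hypoxemia". It is captured from ICD-10-CM codes or EHR data "among the subset of patients with both claims and EHR in the Market Clarity database", if sample size allows.

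A control's index date (Sections 7.2.3 and 7.3) is chosen to resemble the matched patient's time since fibrosing ILD diagnosis, within the same enrollment period. No clinical event anchors it.

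The endpoint's standing varies. The abstract gives "Exposure: oxygen therapy vs no oxygen therapy" and lists as primary outcomes "Time to disease progression; time to all-cause mortality; time to hypoxemia, time to acute exacerbations, counts of acute exacerbations". Section 7.3.3.2 places hypoxemia and acute exacerbations among secondary outcomes. Section 7.1 lists outcomes to be compared between matched cohorts and does not name hypoxemia.

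On covariates, the abstract lists "clinical characteristics (underlying ILD type; respiratory diseases; other clinical characteristics; Quan-Charlson comorbidity score; AHRQ comorbid conditions; smoking; pulmonary rehabilitation", plus demographic and utilization items. Table 1 marks hypoxemia for both baselines as well as for follow-up. Section 7.3.5.3 names four medication classes: corticosteroids, biologics, calcineurin inhibitors and other immunosuppressants. Nintedanib and pirfenidone are not among them.

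**The concern.** Section 5 ties recommendations for long-term oxygen to resting hypoxemia. Some patients will therefore start oxygen because hypoxemia has just been recorded. If that record carries the date of the first oxygen claim, it falls on day 1 of follow-up and meets the endpoint definition at time zero. If the patient was already hypoxemic, the next routine coding after index meets it too. Neither event can be a result of oxygen. Controls have no matching trigger on their assigned date, so the extra events would gather in one cohort.

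The study's stated purpose includes learning whether oxygen leads to better or worse outcomes. An endpoint that can record the reason for treatment as its consequence points toward harm whatever the truth.

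The antifibrotic gap is a separate matter. Section 5 says these drugs slow FVC decline, and Section 7.3.3.1 defines progression by a 10% relative change in FVC. A treatment that the protocol links to that outcome is missing from the named covariates.

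**Working it through.** The plan gives no event rate, effect size or power figure for this endpoint, so there is nothing to reproduce. The check is a reading of the definitions, then an illustration on assumed inputs.

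**What can count as an event**

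- Hypoxemia recorded before index: cannot count. Section 7.3 assesses Aim 2 outcomes in follow-up, which starts on the index date.
- Hypoxemia recorded on the index date: can count, because that date is day 1 and no lag is stated.
- Existing hypoxemia recorded again after index: can count, because no visible rule restricts the analysis to patients free of it.

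Section 7.3.1.1 accepts diagnosis, procedure or revenue codes as evidence of oxygen. An index claim may therefore come from a clinical encounter at which hypoxemia was also coded. This makes a same-day record plausible but does not show how often one occurs.

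**Illustration for index-day events, with no true oxygen effect**

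Let d be the share with an event counted at index and q the later 12-month risk, equal in both cohorts. Then 12-month risk = d + (1 − d)q. All values are assumptions.

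- Starters, d = 0.30, q = 0.20: 0.30 + 0.70 × 0.20 = 0.44.
- Controls, d = 0.05: 0.05 + 0.95 × 0.20 = 0.24. The ratio is 0.44/0.24 = 1.83 and the difference 20 points.
- Controls, d = 0.10: 0.10 + 0.90 × 0.20 = 0.28. The ratio is 1.57.
- Range, with d of 0.10–0.60 in starters and 0.05–0.10 in controls, and q of 0.10–0.30: the lowest ratio is 1.00 (d = 0.10 in both) and the highest is 0.64/0.145 = 4.41.

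A second set of inputs uses a constant later hazard λ, so q = 1 − exp(−λ). Index-day shares are 10%, 30% and 50% in starters against 1%, 2% and 2% in controls. With λ = 0.1 per year the ratios are 1.78, 3.24 and 4.83. With λ = 0.3 they are 1.25, 1.76 and 2.30. With no index-day events the ratio is 1.00 in either setting.

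Re-recording after index is not in these figures.

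**Pairs left after restriction to patients free of hypoxemia**

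Assume that 60–80% of starters and 20–30% of controls are hypoxemic by index.

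- Every hypoxemic patient has a record, statuses independent within pairs: from 0.20 × 0.70 = 14% to 0.40 × 0.80 = 32%.
- The same, but every hypoxemic control is paired with a hypoxemic starter: from 1 − 0.80 = 20% to 1 − 0.60 = 40%.
- Only index-day records (30% and 5%) exclude: 0.70 × 0.95 = 66.5% if independent, 70% if concordant.
- Rarer index-day records (10% and 5%): at least 0.90 × 0.95 = 85.5%.

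**The case against.** Much of the defense has force. Section 7.3.3.2 promises only that time to hypoxemia will be reported, sample size permitting, and Section 7.1 does not list it among compared outcomes. A descriptive report may be all that is intended. That list omits mortality as well, though, so it may not be complete, and the abstract places hypoxemia under the oxygen versus no-oxygen exposure. The intention is unclear, not settled.

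It is also fair that no document figure shows how often hypoxemia is coded on the day oxygen starts. The abstract's rationale gives breathlessness and physical capacity as reasons for oxygen too. The assumed range includes a ratio of 1.00.

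An exclusion could stand in Section 7.3.4 or 7.6.2, neither of which is public. Yet the visible variable definitions carry such rules elsewhere. Time to oxygen initiation is limited to patients without baseline oxygen, and exacerbations have 30-day look-backs and a 14-day merging rule. Hypoxemia has neither. If a rule exists, a cross-reference closes the point.

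A reader might go further and infer that the propensity score leaves out baseline hypoxemia, so that mortality and the other Aim 2 outcomes are confounded. The documents do not support that. The matching procedure is in Section 7.6.2.2, Table 1 already captures hypoxemia at pre-index baseline, and acute respiratory failure, pulmonary hypertension and resource use are listed covariates. Section 7.8 also acknowledges residual confounding. Its remark that matched patients are similar on pre-ILD characteristics, when Section 7.3 provides a pre-index baseline, raises a question about the window but does not establish an error.

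**Conclusion.** The timing point stands on visible text. As defined, the endpoint can count same-day hypoxemia that prompted oxygen, and later re-recording of existing hypoxemia, as outcome events. This would happen mainly in the oxygen cohort. It would be wrong to read the plan as counting pre-index records themselves, since they lie outside the outcome window.

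The consequence applies to this endpoint, and only if the cohorts are compared on it. The direction is toward apparent harm. The size cannot be known from the documents: 44% versus 24% at 12 months is one assumed case, and the two sets of assumptions together span ratios from 1.00 to 4.83. That starters have hypoxemia coded on the index date more often than controls is an inference from the indication in Section 5.

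The antifibrotic omission stands as a gap in the named medication classes. The wording is not strictly exhaustive and the code lists are not shown, and no size can be attached. Use of baseline hypoxemia in matching or adjustment is a query only. This should be fixed before analysis; confidence is medium.

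**What to change.** 1. In Section 7.3.3.2, count hypoxemia events from the day after index in both cohorts. Base any between-cohort comparison on pairs in which neither patient has recorded hypoxemia in the pre-index baseline or on the index date. A one-day lag alone is not enough, because chronic hypoxemia would be coded again. Alternatively, state that the endpoint is descriptive, with no comparison.
2. Reconcile the primary or secondary rank of hypoxemia, and of acute exacerbations, between the abstract and Section 7.3.3.2. State whether hypoxemia belongs with the compared outcomes of Section 7.1.
3. In Section 7.3.5.3, add an antifibrotic class (nintedanib, pirfenidone) to the medication covariates.
4. Query: confirm that Section 7.6.2 uses the pre-index hypoxemia captured in Table 1 for matching or adjustment, and the pre-index rather than the pre-ILD window.

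Cost: the restricted comparison loses pairs and speaks only to patients not hypoxemic at index, which leaves out much of the group for whom Section 5 says long-term oxygen is recommended. It also sits inside the claims-plus-EHR subset. On the assumed figures it keeps about 14–40% of pairs if every hypoxemic patient has a record, about 67–70% if only index-day records exclude, and more if such records are rarer. The descriptive option avoids this loss but gives up the comparison. The antifibrotic class needs one more drug list; the other items are wording.
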